3.10. Visit Windows

Efficacy analysis will be analyzed based on nominal visit. If no nominal assessment exists, but an unscheduled assessment falls into the analysis visit window as defined in Table 3 and the preceding instructions, this assessment will be used. If more than one unscheduled assessment exists in the window, the visit closest to the target date will be used. If there is a tie, the latest value will be used.

Safety analyses will be based on nominal visits, where applicable. Unscheduled safety assessments will not have visit windows applied.

Table 3 Evaluation Intervals for Efficacy Analysis

Nominal Visit	Target Study Day	Protocol-Specified Study Day Window (inclusive)	Interval for Analysis
Screening	NA	-56 to -1	-56 to -1
Week 1 Day 1	1	1 to 1	1 to 1
Week 2 Day 1	8	5 to 11	2 to 15
Week 4 Day 1	22	19 to 25	16 to 29
Week 6 Day 1	36	33 to 39	30 to 43
Week 8 Day 1	50	47 to 53	44 to 57
Week 10 Day 1	64	61 to 67	58 to 71
Week 12 Day 1	78	75 to 81	72 to 85
Week 14 Day 1	92	89 to 95	86 to 99
Week 16 Day 1	106	103 to 109	100 to 120
Week 20 Day 1	134	131 to 137	121 to 141
Week 22 Day 1	148	145 to 151	142 to 155
Week 24 Day 1	162	159 to 165	156 to 169
Week 26 Day 1	176	173 to 179	170 to 183
Week 28 Day 1	190	187 to 193	184 to 197
Week 30 Day 1	204	201 to 207	198 to 211
Week 32 Day 1	218	215 to 218	212 to 225
Week 34 Day 1	232	229 to 235	226 to 239
Week 36 Day 1	246	243 to 249	240 to 253
Week 38 Day 1	260	257 to 263	254 to 267
Week 40 Day 1	274	271 to 277	268 to 281
Week 42 Day 1	288	285 to 291	282 to 295
Week 44 Day 1	302	299 to 305	296 to 309

Week 46 Day 1	316	313 to 319	310 to 323
Week 48 Day 1	330	327 to 333	324 to 333
<hr/>			
<hr/>			
<hr/>			

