7.2 Treatment Discontinuation/ Withdrawal from the Study

7.2.1 Treatment Discontinuation

Treatment discontinuation is defined as any patient who permanently stops receiving study drug. A patient should be discontinued from study treatment if, in the opinion of the Investigator or Sponsor, it is medically necessary, or if it is the wish of the patient.

Patients who prematurely discontinue study drug prior to 48 weeks of treatment will have an EOT (W48D1) visit performed at the time of discontinuation followed by the Safety Follow-up visit within 28 days.

Patients must be discontinued from treatment for any of the following reasons:

- An AE that requires permanent discontinuation of study treatment
- Withdrawal of consent by the patient
- Treatment interruption for > 28 days due to a related AE
- Lack of efficacy
- Disease progression
- Pregnancy
- Patient lost to follow-up
- Investigator decision
- Noncompliance to protocol
- Termination of the study by the Sponsor

44 of 77

AEs leading to the discontinuation of study drug will be followed for 28 days after administration of last dose of study drug or until resolution, resolution to baseline, or until the event is considered stable or chronic.

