1. INTRODUCTION AND OBJECTIVES

1.1. Introduction

Due to the early termination of the current study, this statistical analysis plan (SAP) is created to support an abbreviated clinical study report (CSR), focusing on the primary and secondary endpoints, and the final safety update. Populations for analysis, data handling rules, statistical methods, and formats for data presentation are provided.

This SAP will also outline any differences between the current plan and the study protocol. Any revisions, updates, or differences will be documented and version controlled in the SAP and CSR.

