- a. Informed consent must be obtained before any study-specific procedures are performed. The date of informed consent and W1D1 of study treatment may be a maximum of 56 days apart. The screening period (up to 42 days prior to W1D1 of treatment) starts only after informed consent is obtained AND a study-specific procedure is performed.
- b. W1D1 assessments should be performed prior to study drug administration and may be performed up to 3 days prior (Day -3 to Day -1).
- c. Patients who prematurely discontinue the study during the Primary or Extension Treatment Periods should complete the End of Treatment visit (W48D1) and a Safety Follow-up visit approximately 28 days after last dose of etavopipat (see Table 2).

- d. Recommend vital signs (blood pressure [BP] and heart rate [HR]) to be measured after a patient has rested for at least 5 minutes in the supine or recumbent position. A repeated measurement of HR and BP can be taken within 5 minutes if the first reading is outside the normal range and deemed clinically significant.
- e. Electrocardiograms (ECGs) (12-lead) should be recorded in triplicate. See Protocol Section 8.3.8 for detailed instructions on performing the ECGs.
- f. Adverse events are reported as described in Protocol Section 8.7.5.
- g. Assessments of iron profile (ferritin, transferrin (TIBC) and iron level) will be performed locally and will include the tests listed in Protocol Appendix E (as applicable).
- h. Hematology assessments listed in Protocol Appendix E, may be performed as outpatient/non-study center.
- i. Urinalysis will be performed locally and will include assessment for color and appearance and dipstick analysis for the tests listed in Protocol Appendix E.
- j. Serum pregnancy test will be performed locally at Screening, and a urine pregnancy test may be performed if there is any suspicion of pregnancy during the study, for all female patients of child-bearing potential (see Protocol Section 6.8.1). If a urine pregnancy test is positive, the result must be confirmed with a serum pregnancy test.

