3.2. General Methods

In general, tables will summarize data by transfusion history stratum at Day 1. All statistical analyses will be performed using SAS statistical software Version 9.4 or higher, unless otherwise noted. For categorical variables, descriptive statistics will include frequency count and percentage. If missing is observed, a “Missing” category will be added without percentage. For shift tables, total rows and columns will not include patients from the “Missing” category except the “Missing” column and row and percentage will be calculated based on evaluable patients. For continuous variables, descriptive statistics are number of patients, mean, median, standard deviation (SD), 25th percentile (Q1), 75th percentile (Q3), minimum, and maximum.

For parameters assessed across multiple visits, by-visit summaries will be presented for planned visits from Table 1 and Table 2.

Minimum and maximum values will be presented to the same decimal precision as the raw values, mean, median, Q1, and Q3 values to one more decimal than the raw values, and the SD to two more decimals than the raw values. All percentages will be presented to one decimal place. All p-values will be presented with 4 decimal places and will be shown as ‘<0.0001’ if the value is smaller than 0.0001.

Relative study day will be provided in data listings. Day 1 is defined as the date of first treatment. Other study days are defined relative to Study Day 1. Relative day is calculated as (date of interest - date of the first treatment + 1) for study days on or after the date of the treatment start, and as (date of interest - date of the first treatment) for study days prior to the date of the treatment start.

Figures will be created to plot the data where it is deemed necessary. All data collected on study in the eCRF will be included in data listings.

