4.3. Pharmacokinetic Evaluations

Etavopivat plasma concentrations will be summarized for each transfusion history stratum and overall with descriptive statistics by study visit, and planned collection time (e.g., pre-dose, 1-hour post-dose, etc..) and included in data listings. A line plot of semi-intensive PK concentration data by transfusion history stratum on both linear and semi-log scale will be provided for Day 1 and EOPT.

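### As written, the Week 48 lab, vital-sign and ECG rows pool early-stop visits from any study day with true Week 48 values

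*SAP*

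**What the plan says.** **The label.** Protocol 7.2.1: "Patients who prematurely discontinue study drug prior to 48 weeks of treatment will have an EOT (W48D1) visit performed at the time of discontinuation". Protocol 7.0, the notes to the study schema and footnote c of protocol Table 1-1 agree. Footnote c of SAP Table 1 carries this into the analysis plan: patients who stop during the Primary or Extension period "should complete the End of Treatment visit (W48D1) and a Safety Follow-up visit approximately 28 days after last dose".

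**The analysis rule.** SAP 3.10: "Safety analyses will be based on nominal visits, where applicable. Unscheduled safety assessments will not have visit windows applied". SAP 3.2 adds that "by-visit summaries will be presented for planned visits from Table 1 and Table 2". SAP 4.4.3, 4.4.4 and 4.4.5 summarise laboratory tests, vital signs and ECG by nominal time point. The mean plots of liver tests in 4.4.3 also run over nominal visits. Protocol 9.4 sets nominal visit as the general default. The day-based intervals in SAP Table 3 are titled as intervals for efficacy analysis.

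**PK.** SAP 4.3 gives plasma concentrations with "descriptive statistics by study visit" and planned collection time. W48D1 is a PK visit, with pre-dose, 1-hour and 2-hour samples.

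**Study status.** The SAP was written "Due to the early termination of the current study". SAP 4.1.1 provides a discontinuation reason for patients stopped by that termination.

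**The concern.** The label W48D1 has two meanings: a visit at about Day 330, and the last visit of a patient who stops on any earlier day. Safety summaries keyed to the label, with no check on study day, cannot tell the two apart. Early stopping is expected here, since the study itself was stopped.

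At stake is what the last on-treatment row of the safety tables means. A reader will take it as change from baseline after 48 weeks of drug. If it includes patients who left early for an adverse event or disease progression, it can suggest a late change that is not there, or hide one that is. With about 15 patients planned per stratum and summaries shown by stratum, a few early stoppers could shift a row noticeably.

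**Working it through.** **1. Reproduce the plan's Week 48 day.** Week w Day 1 falls on study day 7 × (w − 1) + 1. For w = 48 this is 7 × 47 + 1 = 330. With the ±3-day visit window the range is 327 to 333. Both agree with SAP Table 3.

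**2. What the label admits.** A true Week 48 visit falls within those 7 days. An early end-of-treatment visit with the same label can fall from about Day 2 to Day 326. For a patient who stops at the Week 6 target, Day 36, the misplacement is 330 − 36 = 294 days, or 42 weeks.

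**3. Look for a rule that separates them.**

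| Place | What it does | Separates early stops from Week 48? |
|---|---|---|
| SAP 3.2 | By-visit tables for planned visits | No |
| SAP 3.10, safety rule | Nominal visits where applicable | No |
| SAP Table 3 | Day intervals, efficacy only | Not for safety |
| SAP 4.4.3 to 4.4.5 | Nominal time point | No |
| SAP 4.3 | Study visit and planned collection time | No |
| SAP 3.2, listings | Relative study day shown | Yes, but in listings only |

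The last rows of Table 3 are empty in the copy read here. Even if they held an end-of-treatment interval, the table's scope is efficacy.

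**4. Size.** With E early stoppers and C completers having such a visit, the share of the row that is not Week 48 is s = E / (E + C). The documents give neither E nor C, so s is unknown.

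To show what a given s would do, assume that early visits are spread evenly over Days 2 to 326, with mean (2 + 326) / 2 = 164, and that completers are at Day 330. The mean actual day in the row is 164s + 330(1 − s):

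| s (assumed) | Mean actual day | Equivalent week, (day − 1)/7 + 1 |
|---|---|---|
| 0% | 330 | 48 |
| 25% | 288.5 | 42 |
| 50% | 247 | 36 |
| 75% | 205.5 | 30 |

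Both the shares and the even spread are assumptions, not estimates for this trial.

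**5. What is not touched.** Adverse event tables count events from first dose to 28 days after last dose. The eDISH plots use peak values. HI-E response is judged on transfusion intervals and measurement dates up to W24D1. None of these depends on the W48D1 label.

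**The case against.** The strongest reply is that pooling is not proven. Protocol 7.0 asks for the assessments scheduled for the end-of-treatment visit, which can be read as a list of procedures rather than a filing rule. SAP 4.4.1.1 treats early discontinuation as stopping before the W48D1 visit, and SAP 4.1.1 distinguishes the Week 48 study visit from the End of Treatment form. On that usage an early stopper never reaches W48D1, and the case report form may use a separate label. This stands as far as it goes: the outcome depends on a form or programming specification outside these documents. It does not settle the point, because the SAP neither says so nor gives the visit a row, and 'where applicable' does not address it.

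Three stronger readings are tempting, and the documents do not support them.

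- *A reader might infer that the last on-treatment values are misreported whichever label is used.* With a separate label, the Week 48 row holds only true Week 48 values. The early-stop values are then absent from by-visit tables but still listed with relative study day.
- *A reader might infer that the Week 48 mean concentration is biased downwards.* Some early-stop samples may come from patients already off drug, for example after an interruption of more than 28 days. But the planned samples are timed to a dose, and the PK Set definition (SAP 2.1) allows case-by-case decisions on inclusion for patients with events that could affect concentrations. Neither the direction nor the size of any bias is established.
- *A reader might infer that Week 48 is the only evidence beyond the 84 days of earlier dosing (protocol 4.2).* Protocol Table 1-1 schedules chemistry and vital signs at Weeks 16, 20, 24, 32 and 40, and ECG at Weeks 16, 24, 32 and 40. All are later than Day 84, and none carries the end-of-treatment label.

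These are also descriptive tables for an abbreviated report, and no test or decision rule uses the row.

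**Conclusion.** The point holds on the plain text. The protocol and SAP Table 1 label the early-stop visit W48D1, SAP 3.10 and 4.4.3 to 4.4.5 summarise safety by nominal visit, and nothing separates the two kinds of visit. Followed literally, the Week 48 rows for laboratory tests, vital signs and ECG pool values from any study day. If the case report form has its own end-of-treatment label, the effect is different and milder: Week 48 is clean, and early end-of-treatment values appear only in listings. The SAP should say which applies.

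The size is unknown, because it equals the early-stop share among patients with such a visit and the documents give no counts. For PK, the conclusion is only that early-stop samples have no stated handling in the W48D1 summary.

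**What to change.** **SAP 3.10.** Limit the Week 48 safety row to W48D1 assessments made at the scheduled time by actual study day: target Day 330, with the protocol window 327 to 333 or a stated, slightly wider interval. The Table 3 analysis interval, 324 to 333, would still drop a visit one day late, on Day 334. Show early end-of-treatment values for laboratory tests, vital signs and ECG in a separate row, 'End of treatment (any time)'.

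Do not re-map these values onto earlier scheduled visits. A Day 36 value would land at Week 6, where no chemistry, vital signs or ECG are planned. Where a scheduled laboratory value already exists, the rule in SAP 4.4.3 of taking the latest non-missing value would let the early-stop value replace it.

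**SAP 4.3.** Exclude samples from early end-of-treatment visits from the W48D1 concentration summary, and list them with time since last dose.

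**Cost.** SAP wording and programming only, with no new data. The Week 48 row will show fewer patients.

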3.11. Futility Assessment

A futility assessment will occur once 15 patients overall or 8 patients in a single transfusion stratum have evaluable responses on the HI-E criteria at W24D1, whichever occurs first.

If the overall futility assessment is performed and ≤ 3 responses are observed, enrollment may discontinue for futility. If there are 4 or more responses at 24-weeks observed, enrollment will continue until a total of approximately 45 response evaluable patients are available at W24D1. A patient with confirmed HI-E response at W16D1 but progression/relapse at W24D1 will be considered a responder for the purposes of the futility assessment.

If the stratum-specific futility assessment is performed and no responses are observed, further enrollment may be restricted to specific subsets of patients based on prior transfusion history.

An informal futility assessment will occur after 15 patients have completed the W24D1 visit or dropped out. The proportion of patients with confirmed HI-E response at any timepoint up to W24D1 will be summarized. Patients discontinuing prior to completing HI-E assessment will be considered non-responders. Additional efficacy and safety data will be summarized for these patients as deemed appropriate.

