3. GENERAL STATISTICAL METHODS

3.1. Sample Size Justification

An overall sample size of N=45 will provide 87.3% power to detect an increase in the response rate for the HI-E criteria. Specifically, the assumed response rates are 40% for the etavopivat intervention and 20% otherwise (null-hypothesis comparator). One-sided testing, a significance level of 0.025, and the exact binomial distribution are used for the calculations.

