3.11.1. Statistical Justification

Assuming the pooled response rate of 40% is met, the probability of incorrectly declaring futility with 15 evaluable patients is 0.0905. This is calculated using the binomial cumulative distribution function with parameters $n=15$, $p=0.4$, $x=3$.

The single stratum futility assessment allows for the possibility that response rates in a single stratum may be lower than 40%, but the pooled response rate after incorporating the other strata could still reach 40%. The per-stratum futility threshold is intended to terminate enrollment in a stratum where the true response rate can be expected to be $<25\%$. Under a binomial distribution with parameters $n=8$ and $p=0.25$, the probability of observing $x=0$ successes is 0.10011.

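### The informal futility look takes the first 15 patients to reach Week 24 or drop out, so it over-samples dropouts and its HI-E proportion is biased downward

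*SAP*

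**What the plan says.** SAP 3.11 describes two looks.

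- **Formal look.** "A futility assessment will occur once 15 patients overall or 8 patients in a single transfusion stratum have evaluable responses on the HI-E criteria". The visit concerned is W24D1, and the earlier of the two triggers applies. Its overall rule is: "If the overall futility assessment is performed and ≤ 3 responses are observed, enrollment may discontinue for futility". SAP 3.11.1 supports that rule with one error rate: "the probability of incorrectly declaring futility with 15 evaluable patients is 0.0905", calculated under a 40% pooled response rate.
- **Informal look.** "An informal futility assessment will occur after 15 patients have completed the W24D1 visit or dropped out". Its outcome is: "The proportion of patients with confirmed HI-E response at any timepoint up to W24D1 will be summarized". Its scoring rule is: "Patients discontinuing prior to completing HI-E assessment will be considered non-responders". Other efficacy and safety data may be summarized for the same patients. No cut-off, decision or error rate is attached.

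Three other places matter. SAP Table 3 puts W24D1 at target Day 162. SAP 1.2.1 says enrollment does not pause during assessments unless the futility analysis suggests a clinical need. SAP 5.2 drops the Interim Assessment Set, so no named analysis set governs the informal look.

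**The concern.** Counting dropouts as failures is a sound, conservative rule when the cohort is fixed in advance, for example by order of first dose. Here membership depends on who resolves first in calendar time, and time to resolution is related to outcome. A dropout can resolve at any time from Day 1, but a patient who stays on treatment cannot resolve for about 23 weeks.

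When the 15th patient resolves, recently enrolled patients who have dropped out are in the set as non-responders. Patients enrolled alongside them who are still on treatment, and perhaps responding, are not. The 15 are therefore not the first 15 treated, and their response rate falls short of the true rate even if the drug performs exactly as assumed.

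At stake is how one reported proportion is read. A figure in the low 30s could be taken as a weak signal when part of the shortfall comes from how the set was chosen.

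**Working it through.** **1. The plan's own figure.** For X ~ Binomial(15, 0.4), P(X ≤ 3) = 0.6^15 + 15(0.4)(0.6^14) + 105(0.4²)(0.6^13) + 455(0.4³)(0.6^12) = 0.0005 + 0.0047 + 0.0219 + 0.0634 = 0.0905. This reproduces SAP 3.11.1, which states it for 15 evaluable patients.

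**2. How many patients are exposed to the selection.** W24D1 falls (162 − 1)/7 = 23 weeks, or about 5.3 months, after first dose. At 1, 2, 3 or 4 patients/month, about 5, 11, 16 or 21 patients start within any such window. Each can enter the set early only by dropping out.

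**3. The link from selection to bias.** Let d be the true dropout rate by Week 24 and s the dropout share among the 15. Fix the response among all dosed patients at 40%. If every dropout is a non-responder, completers respond at 0.4/(1 − d), and the expected proportion in the set is (1 − s) × 0.4/(1 − d). This equals 40% only when s = d. At 3/month with d = 0.30, simulation gives s = 0.41, so the expected proportion is 0.59 × 0.4/0.70 = 0.337.

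**4. Simulation.** *Assumptions, none of them in the documents:* Poisson accrual, dropout uniform over 23 weeks, and the accrual and dropout rates shown. The first 15 by resolution time are compared with the first 15 by enrollment. The low end of each range for the expected proportion scores every dropout as a non-responder. The high end counts as responders those who had confirmed a response before leaving, with confirmation at Week 8 or uniformly over Weeks 8-16.

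| Accrual, dropout | Expected proportion, first 15 to resolve | P(≤3/15), if that rule were borrowed |
|---|---|---|
| 1/month, 10% | 39-40% | 9-10% |
| 2/month, 20% | 37-38.5% | 11-13% |
| 3/month, 30% | 33.5-36.5% | 14-21% |
| 4/month, 30% | 31.5-35.5% | 16-26% |
| First 15 in enrollment order, any setting | 40% | 9% |

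**5. A second dropout model.** With a constant dropout hazard and all dropouts as non-responders, 0.5 patients/week with 10/20/30% dropout gives 38.6/36.7/35.2%. One patient/week gives 36.8/33.6/30.2%. If dropout is confined to the first 8 weeks, the shortfall grows: 29.8% at 1/week with 20% dropout. The direction was downward in all 24 settings tried, while the enrollment-order cohort stayed at 39.8-40.2%.

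**The case against.** The strongest case against concerns consequence and size.

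- **No rule is attached.** A reader might infer that this look decides whether the drug is futile. The documents do not support that. The proportion is only summarized; the ≤3 rule belongs to the formal look, and even there enrollment only *may* stop. The last column of the table therefore rests on a borrowed cut-off. This stands.
- **0.0905 is not wrong.** A reader might also infer that the SAP misstates its false-futility probability. It does not: the figure is tied to 15 evaluable patients and reproduces exactly. This stands.
- **Some dropouts may count as responders.** The outcome is a confirmed response at any time up to W24D1, and an LTB or HTB patient can qualify over any continuous 8 weeks (SAP 4.2.1.1). Treating every dropout as a failure overstates the bias. This stands, and the ranges above allow for it. The bias shrinks but does not vanish.
- **It may be negligible.** With slow accrual and few dropouts it is, as the first row shows.
- **Events have overtaken it.** SAP 1.1 says the plan supports an abbreviated report after early termination. A reader might infer that the biased look led to the termination, but neither document gives the reason. The enrollment decision may well be past, yet the SAP still specifies the summary.
- **The sentence may fix only the timing.** Literally it says when the look occurs. But the scoring of dropouts and the reference back to the same patients make those 15 the natural denominator, and no other set is named.

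**Conclusion.** The point holds as a limited one. As written, the rule over-samples dropouts, and the informal look's HI-E proportion is biased downward whenever accrual is staggered and some patients drop out. The only way to reverse the direction would be for dropouts to respond more often than completers.

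Under a true 40% rate, the shortfall runs from under 1 percentage point (1/month, 10% dropout) to about 4.5-8.5 points (4/month, 30% dropout). These figures rest on assumed accrual and dropout rates and on dropout spread evenly over 23 weeks. Any statement about the chance of 3 or fewer responses also needs the formal look's cut-off to be borrowed.

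The look informs the view of futility but does not decide it. The formal look's error rate is correct. The primary analysis in the Efficacy Evaluable Set does not use this cohort. It is a cheap improvement, not a threat to the trial's main result.

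**What to change.** Replace the trigger sentence and the scoring sentence of the informal look in SAP 3.11 with:

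*The informal futility assessment uses the first 15 dosed patients in order of first dose, summarized when the last of these 15 has completed W24D1 or dropped out; patients who discontinue before completing the HI-E assessment without a confirmed response are non-responders.*

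This names the denominator, restores the expected proportion to the true rate, and settles how a confirmed responder who later leaves is counted.

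If the look has already been run, re-tabulate it in first-dose order and state in the CSR how the 15 were chosen.

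Cost: one SAP sentence, or one re-tabulation. Prospectively, the look would come about 0.2-0.7 month later under the assumptions above, with no extra patients or procedures.
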